## Clinical Investigational Plan

To ensure enrollment balance, each investigational center cannot enroll more than 50% of sample size (23) of each access arm without the prior written approval of the Sponsor.

### 6.4 Justification of Clinical Investigation Design

The Portico valve has demonstrated safety and favorable clinical results via TF access in the TF EU Portico Trial (n=222). The study will evaluate the safety of alternative access for the approved Portico transcatheter aortic and includes a primary safety endpoint of major vascular complications at 30 days. This endpoint is appropriate because vascular access is the only new aspect being investigated in this study and 30-days has been established by VARC2 as the appropriate time period to assess early safety events such as major vascular complications.

Numerous studies have demonstrated that vascular complication rates at 30 days with ALT access are similar to that of the TF approach and that survival at 1 and 2 years is similar between the subclavian and the TF approach. The sample size of 45 subjects is adequate to ensure that the rate of the primary endpoint, major vascular complications at 30 days, is consistent with the rate for Portico valves delivered by TF access as well as with rates reported in the literature.

### 6.5 Timing of Analysis

CE Mark will be submitted for each access route. The analyses for CE Mark report will be conducted separately for each access route on datasets locked after 45 subjects in each access route have had the 30-day study visit (excepting deaths, withdrawals and loss-to-follow-up before 30 days) or crossed the 30-day visit window without a visit (missed visit).

### 6.6 Success Criteria

The study has one primary endpoint without formal hypothesis. The primary endpoint result will be compared with data reported in the literature and is expected to fall within the range of 5-23.3% (pooled estimate 11.9% and CI 8.6%-16.4%).

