#### 4.2 Study Design and Scope

This is a multicenter prospective, non-randomized, 2-arm investigational study without concurrent or matched controls, designed to assess the use of the Portico TF or Alternative Access Delivery System to place a Portico transcatheter aortic valve through an alternative access site, specifically subclavian/axillary or TAO.

A minimum of 45 subjects will undergo transcatheter aortic valve replacement (independent of valve size) via the Portico TF or Alternative Access Delivery System in each arm. A minimum of 45 implants will be accessed via the subclavian/axillary access site arm of the study and a minimum of 45 implants will be accessed via the TAO access site arm of the study. A maximum of 12 investigational sites with prior alternative access technique experience in Europe and will be trained to participate in the study. Enrollment is anticipated to be completed approximately 8 months from the date of first enrollment. Data will be collected at pre-procedure, peri-procedure and at discharge as well as at 30 days, 6 months and 1 year post implantation. All active subjects will be followed for 1 year.

Data from other prospective clinical trials of ALT access in similar patient populations outside of Europe may be included in the analysis and support the submission for CE Mark. CE Mark will be submitted for each access route after implantation and 30 day follow up are completed.

Although the study will not test a hypothesis, the primary endpoint event rate for each cohort will be presented within the context of the range of rates reported for alternative access delivery of transcatheter valves in the literature.

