#### 6.2 Endpoints

##### 6.2.1 Primary Endpoint

The primary safety endpoint is major vascular complications through 30 days, as defined by the Valve Academic Research Consortiumiii (VARC-2) for each access arm of the study.

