### 6.3 Sample Size

The sample size of 45 subjects for each access route is based on the desire to estimate the rate of 30-day vascular complication with a sufficient degree of precision. The rate of major vascular complications at 30 days in Portico TF EU study was 5.9%. The rate of major vascular complications reported for other TAVI valves at 30 days in a weighted meta-analysis of 3,519 patients from 16 studies ranged from 5.0% to 23.3%. The same meta-analysis calculated a major vascular complication pooled estimate 30-day rate of 11.9% (95% CI 8.6%-16.4%). Assuming an event rate of 5.9%, with 45 subjects, the exact 90% CI is (1.45%, 15.32%). Therefore, a sample size of 45 will result in the 90% confidence interval half-width of 9.42% and the 95% upper confidence limit is within the range reported in the literature

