**14.0 Suspension or Premature Termination of the Clinical Investigation**

The Sponsor reserves the right to terminate the clinical investigation at any stage, with appropriate written notice to the investigators, ECs and relevant Regulatory authorities, if required.

A Principal Investigator, EC or regulatory authority may suspend or prematurely terminate participation in a clinical investigation at the investigational sites for which they are responsible. The investigators will follow the requirements specified in the Clinical Trial Agreement.

If suspicion of an unacceptable risk to subjects arises during the clinical investigation in either arm of the study or when so instructed by the EC or regulatory authority, the Sponsor may suspend the clinical investigation while the risk is assessed.

Termination criteria are set based on a maximum allowable number of major vascular complications through 30 days across the two study arms. The study will continue in the arm of the study not under suspension. The Sponsor will terminate the clinical investigation if an unacceptable risk for major vascular complications through 30 days is confirmed with accumulating data as noted in the table below. The termination criterion is selected to be  $x$  events such that the probability of observing  $x$  or more events is  $< 0.05$  assuming that the number of events follows a binomial distribution with event probability 0.119. This event probability is based on the 30-day rate of major vascular complications reported in the literature (see Section 6.3).

If the Sponsor completes an analysis of the reasons for the suspension, implements the necessary corrective actions, and decides to lift the temporary suspension, the Sponsor will inform the Principal Investigators, EC, or regulatory authority, where appropriate, of the rationale, providing them with the relevant data supporting this decision. Approval from the EC or regulatory authority, where appropriate, will be obtained before the clinical investigation resumes. If subjects have been informed of the suspension, the Principal Investigator or authorized designee will inform them of the reasons for resumption.

Number enrolled (n)	Number of events (major vascular complications through 30 days) to	Probability of observing $\geq x$ events
---------------------	--	--

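### The only success criterion for a harm is a two-ended range (5-23.3%): read as the observed rate, 0-2 events in 45 fall outside it and 10 in 45 fall inside it

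*Combined protocol and SAP*

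**What the plan says.** The endpoint is a harm. Section 6.2.1 states: "The primary safety endpoint is major vascular complications through 30 days", for each access arm.

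Section 6.6 is the only text on success. It opens with "The study has one primary endpoint without formal hypothesis" and continues: "The primary endpoint result will be compared with data reported in the literature and is expected to fall within the range of 5-23.3" per cent, adding the pooled estimate of 11.9% and its interval of 8.6% to 16.4%. It does not say whether the result is the observed rate or a confidence limit, and it does not say how a rate below 5% would be viewed.

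Other sections bear on how 6.6 is read:

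- Section 4.2 (repeated in the synopsis) says that "the primary endpoint event rate for each cohort will be presented within the context of the range of rates reported" in the literature. This points to the observed rate.
- Section 6.2.1.1 defines both the observed proportion and an exact binomial 95% upper confidence limit.
- Section 6.3 assumes a rate of 5.9% with 45 subjects and concludes that "the 95% upper confidence limit is within the range reported in the literature". This points to the upper limit.
- Section 14 tabulates termination counts for the same endpoint (6 of 20, 8 of 30, 9 of 40), "assuming that the number of events follows a binomial distribution with event probability 0.119". Section 6.8 says that there are no statistical criteria for termination.

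**The concern.** A success criterion for a complication rate needs one direction: lower is better. A range with a floor at 5% has no such direction. Taken literally, it leaves a very good result outside the criterion and a poor, imprecise one inside it. The ceiling is also compared with a point estimate that carries wide uncertainty at n=45, although the plan already computes the limit that would express that uncertainty.

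At stake is the interpretation of the primary endpoint in each access route's report. If an arm has one event, the written criterion would have to be set aside after the data are seen. If an arm has ten, the report could state that the criterion was met. Prespecification exists to prevent both situations.

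**Working it through.** **Inputs.** n = 45 per arm and assumed rate 5.9% (6.3); range 5-23.3% (6.3, 6.6); exact binomial 95% upper limit (6.2.1.1); termination counts with p = 0.119 and threshold 0.05 (14).

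**Step 1. Reproduce the plan's figures.** The exact (Clopper-Pearson) 90% interval with x = 0.059 × 45 = 2.655 and n = 45 is 1.45% to 15.32%, as 6.3 states. Its upper end is the one-sided 95% upper limit, so that is how the limit is read here. The tails P(X ≥ x) under Binomial(n, 0.119) are 0.0251 for 6/20, 0.0211 for 8/30 and 0.0423 for 9/40, matching section 14.

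**Step 2. Which counts fall in the range?** The exact one-sided 95% upper limit is the 0.95 quantile of Beta(x+1, n−x).

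| Events in 45 | Observed rate | In 5-23.3%? | Upper limit | In 5-23.3%? |
|---|---|---|---|---|
| 0 | 0% | no | 6.44% | yes |
| 1 | 2.22% | no | 10.11% | yes |
| 2 | 4.44% | no | 13.34% | yes |
| 3 | 6.67% | yes | 16.34% | yes |
| 5 | 11.11% | yes | 21.95% | yes |
| 6 | 13.33% | yes | 24.63% | no |
| 10 | 22.22% | yes | 34.77% | no |
| 11 | 24.44% | no | 37.20% | no |

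The observed rate is in range for 3 to 10 events. The upper limit is in range for 0 to 5. The two readings disagree at 0-2 events and again at 6-10.

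**Step 3. How often this matters.** With X ~ Binomial(45, p), the chances for each reading are P(3 ≤ X ≤ 10) and P(X ≤ 5).

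| True rate | Observed rate in range | Upper limit ≤ 23.3% |
|---|---|---|
| 3% | 15% | 99.8% |
| 5.9% | 50% | 95% |
| 11.9% | 90% | 55% |
| 20% | 72% | 9% |
| 23.3% | 51% | 3% |

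At 5.9%, P(X ≤ 2) = 0.4998, so essentially every miss on the observed-rate reading is a miss on the favourable side. These figures ignore any early stop under section 14.

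**Step 4. Against section 14.** The boundaries as rates are 6/20 = 30.0% (outside the range), 8/30 = 26.7% (outside) and 9/40 = 22.5% (inside). The table stops at 40. Carrying the same rule to n = 45 gives 10 events (P = 0.0361), or 22.2%, also inside. That last boundary is an extension made here and is not in the plan.

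**Step 5. The literature range.** Section 4.2 promises context "within the context of the range of rates reported for alternative access delivery of transcatheter valves in the literature". Section 6.3 describes 5.0-23.3% as rates for other TAVI valves, with no restriction to alternative access.

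**The case against.** The strongest reply is that 6.6 is not a decision rule. The study disclaims a formal hypothesis, says only what is expected, and is sized for precision: "The sample size of 45 subjects for each access route is based on the desire to estimate the rate". Nothing states that a rate below 5% is a failure, and the CE Mark submission is tied to implantation and 30-day follow-up, with no reference to 6.6. This stands, and it limits the severity. It does not remove the defect, because a descriptive benchmark under a success heading still needs a direction and a defined quantity.

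A second reply is that the result in 6.6 may mean the upper limit, as 6.3 suggests. Then 0-2 events are inside the range, 10/45 is outside, and the problem largely disappears. The documents allow this reading, although 4.2 and the synopsis favour the observed rate. Because the two readings conflict, the plan has to say which one applies.

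Third, a reader might infer that any result meeting the termination rule would also count as success. The documents do not support that. Only one of the three tabulated boundaries lies in the range, and section 14 leaves unclear whether its counts are per arm or pooled, whereas 6.6 concerns each arm. If they are per arm, an arm at 9/40 could be stopped before 45 subjects are analysed, so some of the in-range chance at high true rates in step 3 would not be realised.

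Finally, 6.4 partly bridges the literature mismatch by stating that vascular complication rates are similar for alternative and transfemoral access. That makes the mismatch a minor alignment point.

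**Conclusion.** The concern holds as a should-fix. Section 6.6 sets a two-ended range for a harm and does not say which quantity is compared with it. On the observed-rate reading, 0-2 events in 45 fall outside, with about a 50% chance at the planning rate, and 10/45 falls inside with an upper limit of 34.8%. On the upper-limit reading both answers reverse. The 22.5% termination boundary at n = 40 also lies inside the range for the observed rate.

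These sizes assume exactly 45 analysed subjects per arm (45 is a minimum), independent binomial outcomes and a one-sided 95% limit.

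Two stronger conclusions do not follow. One is that a low complication rate would formally fail the study or block CE Mark submission; no section attaches that consequence. The other is that the plan needs a hard pass mark such as an upper limit at or below 23.3%. That figure is the highest rate in the cited range and is not a stated performance goal. As a pass/fail rule it would fail about 45% of the time at a true 11.9%, in a study that disclaims testing.

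**What to change.** Amend 6.6 as follows:

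- Remove the 5% lower bound and state that lower rates are favourable.
- State that the quantity compared with the upper end of the literature range is the exact 95% upper confidence limit from 6.2.1.1, consistent with 6.3. Report it beside the observed rate for each arm, at the actual number analysed, descriptively and with no formal test. For information, at n = 45 the limit is 21.95% for 5 events and 24.63% for 6.
- Cite the same literature range in 4.2 and 6.6, or label 5-23.3% as rates for other TAVI valves.

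Separately, the termination table in section 14 must be reconciled with 6.6 and with 6.8, and its scope (per arm or pooled) stated. Which rule should govern is for the sponsor to settle.

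The cost is an amendment to the wording, with ethics committee approval and regulatory approval where applicable (Appendix B), and no extra subjects. The downside is a comparison that looks less favourable: at a true rate of 11.9%, the upper limit is at or below 23.3% about 55% of the time, against 90% for the observed rate falling in range.

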### 6.7 Interim Analysis

No interim analyses are planned for this study.

### 6.8 Statistical Criteria for Termination

There are no statistical criteria for termination of this study.

### 6.9 Deviations from Statistical Plan

If any deviations from the original statistical plan occur, such deviations will be documented in the clinical study report or statistical report containing the analysis results.

## 7.0 Study Committees

### 7.1 Clinical Event Committee (CEC)

An independent CEC will be established for the trial. The primary function, responsibilities and membership will be described in detail in a CEC charter.

### 7.2 Subject Selection Committee

The Subject Selection Committee will consist of cardiac surgeons and interventionalists who will be responsible for ensuring subject eligibility for implant according to the protocol. After study

## Clinical Investigational Plan

Informed Consent Form and Data Protection Form are obtained and study eligibility is confirmed, subject data will be reviewed by the Subject Selection Committee prior to the implant procedure to confirm, risk assessment, echo and CT measurements. CT Imaging, will be reviewed to ensure acceptable annular measurements for the Portico Transcatheter Heart Valve.

The Subject Selection Committee's decision on whether to include the subject in the study must be documented and communicated to the enrolling site by the Sponsor. If the Subject Selection Committee considers the subject ineligible for implant, the subject will be withdrawn from the study and the reason for exclusion documented.

The membership and process is further defined in the Subject Selection Committee Charter.

### 8.0 Risks and Benefits of the Clinical Study

#### 8.1 Anticipated Clinical Benefits

There are no guaranteed benefits from participation in this study. Implantation of the transcatheter heart valve in the annular position may result in one or more of the following: improved valvular function, acute alleviation of symptoms related to aortic stenosis, improved morbidity and mortality. In addition, these or additional benefits may occur to future subjects through experience gained in this clinical study.

#### 8.2 Anticipated Adverse Events and Adverse Device Effects

Anticipated adverse events associated with any transcatheter aortic valve placement may include, but are not limited to:

1. Access site complications (e.g., pain, bleeding, infection, hematoma, pseudoaneurysm, etc.)
2. Acute coronary obstruction
3. Acute myocardial infarction
4. Access site injury
5. Allergic reaction to antiplatelet agents, contrast medium, anesthesia, or valve components
6. Anaphylactic shock/toxic reaction
7. Annulus rupture
8. Aortic rupture
9. Ascending aorta trauma
10. Atrio-ventricular node block
11. AV fistula
12. Bleeding
13. Cardiac arrhythmias
14. Cardiovascular or vascular injury, such as perforation or damage (dissection) of vessels, ventricle, myocardium or valvular structures that may require intervention
15. Conduction system injury
16. Death
17. Endocarditis
18. Embolism: air, calcification or thrombus
19. Exercise intolerance (weakness)
20. Fever
21. Heart failure
22. Hematoma
23. Hemodynamic compromise

**Clinical Investigational Plan**

24. Hemolysis
25. Hemolytic anemia
26. Hemorrhage
27. Hypotension or hypertension
28. Immunological reaction
29. Infection
30. Leakage, regurgitation
31. Left ventricular failure/rupture
32. Left ventricular impairment (due to apical scar)
33. Myocardial ischemia
34. Mitral valve insufficiency
35. Multi-organ failure
36. Neurological changes including stroke/transient ischemic attack;
37. Non-structural dysfunction (i.e., entrapment by pannus, paravalvular leak, inappropriate sizing or positioning)
38. Pannus
39. Paravalvular leak
40. Pericardial effusion
41. Perforation of the myocardium or a blood vessel
42. Potential coronary obstruction
43. Renal failure
44. Renal insufficiency
45. Respiratory failure (shortness of breath)
46. Sepsis
47. Septal rupture
48. Stenosis (high gradient)
49. Stroke
50. Structural valve deterioration (i.e., calcification, leaflet tear)
51. Systemic peripheral ischemia
52. Tamponade
53. Valve explant
54. Valve embolization
55. Valve migration or malposition
56. Valve stenosis
57. Valve thrombosis
58. Ventricular failure (acute)
59. Ventricular rupture
60. Vessel dissection or spasm

It is possible these complications could lead to:

- Transfusion
- Conversion to open surgical procedure
- Reoperation or re-intervention
- Emergent balloon valvuloplasty
- Emergent percutaneous coronary intervention (PCI)
- Emergent surgery (i.e., coronary artery bypass, heart valve replacement)
- Explantation of the valve

**Clinical Investigational Plan**

- Permanent Disability
- Death
- Permanent Pacemaker implantation
- Valve in valve implantation

There are no known interactions of the Portico TF or ALT Delivery System with concomitant medical treatment.

Subjects experiencing an adverse event shall be treated per the standard of care at the investigation site.

There may be additional risks that are unknown at this time and risks that are unanticipated. Further study related tests which are not standard of care for a TAVI procedure have added risks which may include:

Six minute walk test: the possible risks from this test are that the subject may experience fatigue, shortness of breath, chest pain and/or leg cramps. This test is done under the supervision of a trained professional in a testing area where medical care is immediately available. The test will be immediately stopped if the subject experiences chest pain, intolerable shortness of breath, leg cramps or pale appearance.

Blood work: the risk of inserting a needle into a vein in the subjects arm may include temporary discomfort from the needle stick. There is also a small risk of infection, bruising, swelling, bleeding or fainting. These risks are minimized by cleansing the site carefully prior to obtaining the blood sample and applying pressure to the site after the blood sample is obtained.

Echocardiogram: a lubricant (gel) is used on the skin to improve picture quality and this may feel cold. There are no known risks associated with receiving an echocardiogram there may be discomfort from the pressure of the transducer as the images are taken.

### **8.3 Residual Risks Associated with the Device Under Investigation**

An analysis of the risks associated with the design of the TF and ALT Delivery systems have been performed.

The benefit of using a transcatheter aortic valve via alternative access in high-risk and/or inoperable patients outweighs the residual risks associated with TAVI treatment. The inoperable patient population is at an increased risk of death despite maximal medical therapy. In clinical practice, at least 30% of the high-risk patient population with severe aortic stenosis does not undergo surgery, so TAVI provides a less invasive treatment option, with similar outcomes to surgery.

The unique features of the TF and ALT Delivery systems include the ability to resheath, reposition, and redeploy to allow for optimal placement at the implant location prior to full deployment. These design features may reduce the risk of adverse events related to misplacement and adjustments made post implant.

Abbott's final opinion is that the residual risks associated with the TF and ALT Delivery systems are outweighed by the potential benefit for use in patients with an increased risk of death despite maximal medical therapy.

## Clinical Investigational Plan

### 9.0 Requirements for Investigator Records and Reports

#### 9.1 Deviations from CIP

A deviation is defined as an event where the clinical investigator, site personnel, Sponsor or Sponsor representative did not conduct the clinical study according to the Clinical Investigational Plan, EC requirements or the Investigator Agreement.

Deviations from the CIP should be avoided, except in cases where the investigator determines that adhering to the CIP might expose the subject to unreasonable risks.

Regulations require that the PI maintain accurate, complete, and current records, including documents showing the date of and reason for every deviation from the Clinical Investigational Plan. Relevant information for each deviation will be documented on a Deviation Case Report Form. The site will submit the CRF to Abbott.

Regulations require Investigators obtain approval from Abbott and the EC [as required] before initiating changes in or deviations from the protocol, except when necessary to protect the life or physical well-being of a subject in an emergency. Under emergency circumstances, deviations from the CIP to protect the rights, safety and well-being of human subjects may proceed without prior approval of the Sponsor and the EC. Such deviations shall be documented and reported to the Sponsor and the EC as soon as possible, but no later than 5 working days.

Prior approval must be requested when the PI anticipates, contemplates, or makes a conscious decision to depart from the CIP, except when unforeseen circumstances are beyond the Investigator's control (e.g. a subject who fails to attend a scheduled follow-up visit, a subject is too ill to perform a CIP-required test, etc.). All deviations, including those beyond the Investigator's control, must be reported on a CRF.

To obtain approval, the Principal Investigator may call or email and discuss the potential deviation with Abbott or designee prior to initiating any changes.

All deviations must be reported to appropriate regulatory authorities in specified timelines (if appropriate).

